- a) Obesity is a well-known epidemic in the US with prevalence nearing 40%. [1] Obesity is a risk factor for a myriad of disease states including osteoarthritis (OA) due to increased load on the weightbearing joints. Therefore, patients with obesity, and namely those with body mass index (BMI) approaching $>40\text{kg}/\text{m}^2$ (class III obesity), suffer from OA disproportionately compared to their non-obese peers. [2] As this population frequently reports to arthroplasty clinics, studies have identified increased rates of post-operative complications following total joint arthroplasty (TJA) specifically in the class III obese population. [2-5] To combat this increased risk, arthroplasty surgeons traditionally have excluded this population from their surgical practice or encouraged their patients to lose weight in order for their BMI to drop below $40\text{kg}/\text{m}^2$; however, these practices have been recently questioned. [6-8]

With the validity of lowering BMI to improve TJA outcomes being questioned, studies have made efforts to identify more patient-specific factors such as body composition. Body composition can be identified through several modalities including anthropomorphic measurements, DEXA, MRI, and CT. [9-11] In addition, bioimpedance

analysis (BIA) offers rapid, accurate, and non-invasive assessment without the use of ionizing radiation. [9, 12, 13] BIA can be completed through multiple devices including a stationary, scale-like device, a portable ECG-like device, or even wearable wristbands.

Our group has conducted numerous studies focusing on body composition in arthroplasty patients, including changes they experience following surgery and pre-operative risk identification. By employing both clinic-based and home-based assessments more frequently than patients would normally have, this study aims to identify any benefit, if any, a wearable BIA device serves in an obese-arthroplasty population.

3) Study Aims

- a) Aims:
 - i) To identify if the use of a wearable BIA wristband aids in the desired body composition changes (body mass loss, fat mass loss, skeletal muscle mass gain)
 - ii) To quantify the body composition changes exhibited by each cohort
 - iii) To track surgical outcomes for those patients that are indicated for total joint arthroplasty
- b) Hypotheses:
 - i) The wearable group will exhibit the desired body composition changes more rapidly than the control group

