 - ii) The wearable group will exhibit greater desired body composition changes more rapidly than the control group
 - iii) The wearable group will less post-operative complications than the control group

4) Administrative Organization

- a) This study will solely be completed at the University of Iowa Healthcare and Clinics Department of Orthopaedics and Rehabilitation.

5) Study Design

- a) Experimental design of the study: randomized controlled trial with single blinding
- b) Study population general description
 - i) Specify total number of adult subjects, age range and percent by gender
 - (1) 90 subjects (>18 years old)
 - (2) 50% male, 50% female
 - ii) Specify total number of minor subjects (less than 18 years of age), age range and percent by gender.
 - (1) none
- c) Sample size determination and power analyses
 - i) A power analysis was performed by the orthopedic department statistician [name].
- d) Study outcomes/endpoints
 - i) Primary outcomes
 - (1) Muscle mass, body mass, and fat mass changes from baseline at 3-, 6-, 9-, and 12-months
 - ii) Secondary outcomes
 - (1) Time to achieve desired body composition changes
 - (2) Time to TJA indication
 - (3) Surgical outcomes for those that undergo TJA

6) Study Procedures

- a) Describe Subject selection procedures
 - i) Describe the sampling plan including Inclusion/Exclusion criteria (subject and disease characteristics)
 - (1) Inclusion Criteria
 - (a) Adults > 18 years
 - (b) BMI > 40kg/m2
 - (c) Presenting to arthroplasty-obesity clinic with desire for total joint arthroplasty procedure
 - (d) Owns a smartphone capable of handling iOS or Google Play apps
 - (2) Exclusion Criteria
 - (a) Has a pacemaker or other electronic pacemaker placement
 - (b) Inability to complete study protocols
 - (c) Inability to stand unsupported for 60-90 seconds
 - ii) Indicate if the study plans to enroll non-English speaking subjects. If so, specify language(s), who will translate documents, who will serve as a translator. The IRB must review and approve all translated documents.
 - (1) This group will not be enrolled
 - iii) Indicate if the study will enroll subordinates of the PI or a member of the research team.
 - (1) This group will not be enrolled
 - iv) Indicate if the study will enroll pregnant women for research on fetuses and neonates
 - (1) This group will not be enrolled

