 - (a) If patients are randomized the wearable group, they will be provided a wearable and instructions on installing the app and its features. They will be instructed to take BIA measurements at least weekly via the wearable. The wearable group will be instructed at the beginning of each visit to remove and keep their wearable out of sight of the PI during their visit.
 - (4) Patients who enter “Surgical” period

- (a) Patients who are indicated for TJA (at the PI's discretion) will leave the coaching period and enter the surgical period. Patients' medical record will be followed if they are indicated for TJA for post-operative outcomes such as infection, reoperation, implant failure. Surgical follow-up will occur for up to 24 months following study enrollment.
- ii) Provide a schedule of all study assessments and subject activities, including a tabular representation or timeline as applicable
 - (1) See **Table I** below
- h) Recontacting Subjects Lost to Follow Up – Indicate if the researcher will attempt to locate subjects if the research team is unable to reach them through the contact information they provided. Describe the procedures and justification for these efforts to locate subjects.
 - i) Research members will not contact the patients lost to follow, as standard clinic procedures have nursing staff contact the patients.
- i) Subject Compensation
 - i) Specify compensation method(s)
 - (1) Patients will not be compensated monetarily. Those randomized to the study cohort will be able to keep their wearable device, if desired.
 - ii) Describe the compensation plan, including amount per visit, total compensation amount, pro-rating for early withdrawal
 - (1) N/A
 - iii) Indicate whether the study will use the departmental cash handling plan or obtain approval from Accounting Services for a study-specific cash handling plan.
 - (1) N/A

7) Privacy and Confidentiality Protections

- a) Describe privacy protections – collecting data in a private space, collecting the amount and type of information you need to answer your research question(s)
 - i) Only the minimum necessary data will be collected. The data collected will be done in a private clinic room.
- b) Describe plans and justification for collecting social security number (SSN)
 - i) N/A

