- c) Confidentiality / Data Security Plans – Refer to the Data Security Educational Tool and the Protecting Sensitive Data page of the UI ITS website. Specify plans for transmitting, transporting and/or storing:
 - i) Paper records
 - (1) Informed consent documents to be kept in PI's locked office
 - ii) Electronic records - Specify who is responsible for maintaining security. Researchers are advised to consult with the departmental IT representative to establish a data security plan that is appropriate to the level of security of the data being collected/stored for the project.
 - (1) Standard protections on departmental server
 - iii) Biospecimens - Specify who is responsible for maintaining security.
 - (1) N/A
- d) Plans for sharing data or taking data outside the UI
 - i) N/A

8) Risks and Benefits

- a) Describe all possible risks (physical, emotional or psychological, financial, legal or social risks).
 - i) Risks include loss of information/privacy, falling off stationary BIA scanner, hand pain from hand grip strength testing.
- b) Describe all steps to minimize any possible risk to subjects.
 - i) Data will only be accessed by need-to-know study members, a study team member will supervise and “spot” the subject on the stationary BIA scanner, patient will be advised to take rests in between hand grip strength testing to minimize pain.
- c) Describe all guaranteed direct benefits to subjects (do not include compensation or hypothesized results).
 - i) None
- d) Describe potential benefits to society from the results of the research.
 - i) Future patients will benefit from knowing if wearable technology has an effect or not.

9) Safety Monitoring Plan

- a) N/A

10) Data Analysis Plan

- a) Describe statistical analysis methods as appropriate. Consult with a biostatistician, if appropriate. The analysis plan should correspond with the data collection described in the Study Procedures section. Describe plans for intent-to-treat methodology and any sample stratification.
 - i) Noninferiority comparison of the primary outcome and secondary outcome between the treatment groups at each time points.
 - ii) Multivariate analysis to compare patient demographics between the two treatment arms.
 - iii) Non-parametric tests such as ANOVA and ANCOVA will be utilized to determine if there is any difference between the two groups.
- b) Provide the rationale or power analysis to support the number of subjects proposed to complete the study.

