Group sample sizes of 44 in the treatment and control arm achieve 80% power to detect a difference of 1.676 in a design with 5 repeated measurements having a compound symmetry covariance structure when the standard deviation is 3.610, the correlation between observations on the same subject is 0.500, and the alpha level is 0.050

11) Tables and Figures

Table I. Schedule of study procedures.

Study Period	Coaching ^a													Surgical ^a
	V1	V2	V3	V4	V5	V6	V7	V8	V9	V10	V11	V12	V13	
Visit Number	0	1	2	3	3	4	6	7	8	9	10	11	12	Until Month 24
All Patients														
Screening	X													
Consent	X													
Randomization	X													
Clinic Education ^b	X			X			X			X				X
Stationary BIA ^b	X			X			X			X				X
Handgrip Strength ^b	X			X			X			X				X
Phone Visit		X	X		X	X		X	X		X	X		
Wearable Group														
Wearable Distribution	X													
Wearable Compliance Check		X	X	X	X	X	X	X	X	X	X	X	X	
Surgical Outcomes Check^c														
^a Patients may exit the Coaching period and enter the Surgical period at any time point														
^b Standard protocol for all patients presenting to arthroplasty-obesity clinic														
^c Only for study group														
^d Only for subjects that undergo TJA. Will occur via EMR rather than direct patient contact.														

12) Literature Citations

1. Obesity: preventing and managing the global epidemic. Report of a WHO consultation. World Health Organ Tech Rep Ser 894: i, 2000
2. Obesity and total joint arthroplasty: a literature based review. In: J Arthroplasty. United States: 2013 Elsevier Inc. 714. 2013

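### Hypothesis iii, and hypothesis i on its natural reading, claim benefit on secondary outcomes that section 10(a) tests beside the primary with no order, alpha split or exploratory label

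*Combined protocol and SAP*

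**What the plan says.** Section 5(d) ranks the outcomes. The primary outcomes are changes in muscle, body and fat mass at 3, 6, 9 and 12 months. The secondary outcomes are three: "Time to achieve desired body composition changes", time to TJA indication, and surgical outcomes in those who undergo TJA. Section 6(g)(i)(4) describes the last of these only by example, as "post-operative outcomes such as infection, reoperation, implant failure".

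Section 3(b) states the hypotheses. Hypothesis i reads "The wearable group will exhibit the desired body composition changes more rapidly than the control group". Hypothesis iii reads "The wearable group will less post-operative complications than the control group". Time to TJA indication appears in no hypothesis.

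Section 10(a)(i) gives one instruction for both tiers: "Noninferiority comparison of the primary outcome and secondary outcome between the treatment groups at each time points". Section 10(a)(iii) adds tests for any difference between the groups. The only significance level is in the power statement in section 10(b), where "the alpha level is 0.050". The protocol gives no testing order, no condition on the primary result, no division of alpha and no exploratory label.

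**The concern.** Secondary outcomes are often left unadjusted because readers take them as supportive. Here two of the three hypotheses point at them. Hypothesis iii can be answered only from the surgical outcomes, and hypothesis i is most directly answered by the time to desired change. Section 10(a)(i) then treats primary and secondary outcomes alike.

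Under that plan, the trial could miss on all three masses and still report faster change or fewer complications as a confirmed hypothesis, on one nominal p-value among several. The evidence behind such a claim would also be thin. The only power statement concerns a difference in means over repeated measurements. Complications are observed only in the patients who go on to TJA, a subset of the 90 enrolled that forms after randomisation.

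**Working it through.** **1. What level does the stated 0.050 refer to?** The inputs are from section 10(b): difference 1.676, SD 3.610, five measurements, correlation 0.500, power 80%, 44 per arm.

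- SD of a patient's mean over five compound-symmetric measurements: 3.610 × √((1 + 4 × 0.5)/5) = 2.796.
- n per arm, two-sided 0.05: 2 × (1.960 + 0.842)² × 2.796² / 1.676² = 43.7, so 44. This reproduces the plan's figure.
- n per arm, one-sided 0.05: 2 × (1.645 + 0.842)² × 2.796² / 1.676² = 34.4, so 35. This does not.

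The stated 0.050 is therefore two-sided for the power calculation. Carrying it over to the secondary tests is an assumption, because the protocol gives no level for them.

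**2. Chance of at least one false positive with no true difference.** For k independent tests at level α it is 1 − (1 − α)^k:

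- Three listed secondary outcomes: 1 − 0.95³ = 0.143.
- Hypotheses i and iii only: 1 − 0.95² = 0.098.
- Three tests, counting only errors that favour the wearable: 1 − 0.975³ = 0.073, against 0.025 for one test.

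For correlated tests, equicorrelated normal test statistics were simulated (2,000,000 draws, critical value 1.96):

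| Tests counted | r = 0 | r = 0.5 | r = 0.8 |
|---|---|---|---|
| Three, either direction | 0.143 | 0.125 | 0.098 |
| Hypotheses i and iii, either direction | 0.098 | 0.090 | 0.078 |
| Three, favouring the wearable only | 0.073 | 0.063 | 0.049 |

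**3. A case closer to this trial.** Section 6(g)(i)(2) links TJA indication to reaching the body composition goals, so the two time outcomes are probably strongly correlated. Surgical events arise only in those operated on, so that test may be sparse and have a true size well below 0.05. Assume r = 0.8 between the time outcomes and an independent surgical test of true size 0.01:

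- Two time outcomes: 0.078. With the surgical test: 1 − (1 − 0.078) × 0.99 = 0.087.
- Hypotheses i and iii only: 1 − 0.95 × 0.99 = 0.0595.

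**4. Test type.** These figures treat the tests as superiority tests, which is what the hypotheses claim. Section 10(a)(i) says noninferiority and gives no margin. That is a separate defect, and it supplies no error control for the secondary outcomes.

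**The case against.** A reader might infer that a false claim from the secondary outcomes is two to three times as likely as the stated 0.05. The documents do not support that. The ratio comes from three tests counted in either direction (0.098/0.05 = 2.0 to 0.143/0.05 = 2.9), but the hypotheses are directional and a result favouring control confirms none of them. In the wearable's favour the rate is 0.049 to 0.073, which is 1.0 to 1.5 times 0.05. It is two to three times only the matching one-test rate of 0.025. Nor would every significant secondary result confirm a hypothesis, since time to TJA indication is in none.

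Larger figures are also tempting. Five tests, with surgical outcomes split into three complications, give 0.183 at r = 0.5. Eight tests, with two time outcomes at four visits, give about 0.17 to 0.27. The first gives each possibly sparse complication test its full 0.05 size and relies on an illustrative list. The second takes a general sentence to mean that time-to-event outcomes are tested separately at every visit. Neither is needed for the point.

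Three further objections have weight. Speed of change could be judged from the primary outcome at successive visits, so tying hypothesis i to the secondary outcome is a natural reading but not the only one. Aim iii is only to track surgical outcomes. Section 5(d) does separate primary from secondary, and nowhere does the protocol say that a nominal secondary result would count as confirmatory.

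These objections limit the size of the problem but do not remove it. Hypothesis iii has no basis except a secondary outcome, and section 10 does not carry the ranking in section 5(d) into the testing.

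**Conclusion.** The concern holds at moderate size. The plan allows a nominal secondary result to stand as confirmation of hypothesis iii and, on its natural reading, of hypothesis i, with no control or label.

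With one test at two-sided 0.05 for each listed secondary outcome, the chance of at least one false positive in either direction is about 0.10 to 0.14 for correlations from 0.8 down to 0. It is about 0.09 in the case with correlated time outcomes and a sparse surgical test. For hypotheses i and iii alone it is about 0.06 to 0.10. Counting only errors favouring the wearable, three tests give about 0.05 to 0.07 against 0.025 for one.

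The absence of any rule is plain from the text. The size rests on the assumed number of tests, their level, their correlation and, in the lower cases, an assumed surgical test size of 0.01.

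**What to change.** Add to section 10(a) that each time outcome is compared between arms once, over the whole coaching period, and not visit by visit. Add that all secondary outcomes, including surgical outcomes in those who undergo TJA, are exploratory and are reported as estimates with 95% confidence intervals without a claim of significance. Reword hypothesis iii, and hypothesis i so far as it rests on time to change, to match. An exploratory hypothesis iii also fits aim iii better.

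If the investigators want a formal claim on a time outcome, a fixed testing order conditional on the primary could be used, but only once a single primary comparison has been defined. The primary is now three masses at four time points, so there is no one result to condition on.

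The cost is a few sentences in sections 3(b) and 10(a), with no new data or patients. The downside is that a nominally significant secondary result, including one on speed of change, can be reported only as hypothesis-generating.

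### The 80% power in 10(b) belongs to a five-measurement average, not to the planned comparison at each visit, where power is about 59–60% unadjusted or 71–72% baseline-adjusted

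*Combined protocol and SAP*

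**What the plan says.** The power statement is in section 10(b): "Group sample sizes of 44 in the treatment and control arm achieve 80% power to detect a difference of 1.676". It assumes a calculation "in a design with 5 repeated measurements having a compound symmetry covariance structure", "when the standard deviation is 3.610", a within-subject correlation of 0.500 and alpha 0.050. It does not name the outcome or units. It also does not say whether the SD is of raw values or of changes, or whether the test is one- or two-sided.

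Section 5(b) plans "90 subjects (>18 years old"), which is 45 per arm at equal allocation. Section 5(d) defines the primary outcomes as changes from baseline in muscle, body and fat mass at 3, 6, 9 and 12 months.

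Section 10(a)(i) describes the analysis as "Noninferiority comparison of the primary outcome and secondary outcome between the treatment groups at each time points", with no margin. Section 10(a)(iii) names ANOVA and ANCOVA, without covariates and without a primary contrast.

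On exit, footnote a of Table I says "Patients may exit the Coaching period and enter the Surgical period at any time point". Section 6(g) says the same and links the indication for surgery to reaching body composition goals. Under section 6(h) the study team does not recontact patients lost to follow-up; that is left to clinic nursing staff. No exit or dropout rate, no inflation, and no rule for primary-outcome data after exit is given.

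**The concern.** A power figure is informative only for the analysis it was computed for. Averaging five correlated measurements reduces the variance to 60% of the single-measurement value, and the stated sample size uses all of that gain. A comparison at one visit gets none of it.

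The count of five also fails to match the endpoint. Five can be reached only by including the V1 baseline, which precedes any use of the wearable. Change from baseline has four values per patient.

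Finally, the margin between patients enrolled and patients needed is two, in a trial whose own procedures move patients out of the coaching period.

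At stake is how a null result is read. If no difference is found at a given visit, readers would take it as coming from an 80%-powered comparison, when the power on the protocol's inputs was well below that.

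**Working it through.** **Inputs**, all from section 10(b) unless noted: difference d = 1.676; SD = 3.610, so SD² = 13.032; correlation ρ = 0.5, compound symmetry; alpha 0.05, taken as two-sided; 44 per arm, or 45 per arm from the 90 in section 5(b).

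**Formula.** Power = Φ(d / √(2V/n) − 1.96), where V is the per-patient variance of the quantity compared.

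**1. Reproducing the plan's figure.** For the mean of five measurements, V = SD² × (1 + 4 × 0.5)/5 = 0.6 × 13.032 = 7.819. The sample size needed is 2 × 7.819 × (1.960 + 0.842)² / 1.676² = 43.7, so 44 per arm. At 44, √(2 × 7.819/44) = 0.596, 1.676/0.596 = 2.811, and power = Φ(0.851) = 80.3% (79.4% with the noncentral t). A one-sided test would need only 35 per arm, so the stated figure is two-sided.

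**2. One visit, unadjusted.** The variance of a change is V = 2 × SD² × (1 − 0.5) = SD² = 13.032. This equals SD² whether 3.610 describes raw values or changes, so the unclear SD does not matter here. At 44, 1.676/0.770 = 2.178 and power = Φ(0.218) = 58.6%. At 45 it is 59.6%. Reaching 80% would take 73 per arm.

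**3. One visit, adjusted for baseline** (3.610 read as the SD of raw values). V = SD² × (1 − 0.25) = 9.774. Power is 71.0% at 44 and 72.0% at 45.

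**4. Mean change over four visits, unadjusted.** V = SD² × [(1 + 3 × 0.5)/4 + 1 − 2 × 0.5] = 0.625 × 13.032 = 8.145. Power is 78.7% at 44 and 79.5% at 45; 46 per arm are needed for 80%.

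**5. Mean of four visits, adjusted for baseline** (same reading of the SD). V = SD² × (0.625 − 0.25) = 4.887. Power is 94.5% at 44 and 89.6% at 36; 28 per arm are needed for 80%.

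**6. Loss.** The allowance is 2/90 = 2.2%. The rates below are assumptions, because the documents give none.

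| Assumed loss from 90 | Five-visit average, lost patients give no data | Four-visit mean change, partial data used |
|---|---|---|
| 10% | 77% (40.5 per arm) | 78–79% |
| 20% | 72% (36 per arm) | 76–78% |
| 30% | 66% (31.5 per arm) | 74–77% |

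The last column assumes 45 per arm, a constant effect, non-informative exit and exits spread evenly over the year. The higher value has everyone seen at month 3; the lower lets exit precede month 3. A patient with k visits contributes 1/[SD² × (1 + (k − 1) × 0.5)/k]. For 30% with exit from the start, the information per arm is 45 × (0.075/1 + 0.075/0.75 + 0.075/0.667 + 0.70/0.625)/13.032 = 45 × 1.4075/13.032 = 4.860. Then 1.676/√(2/4.860) = 2.613 and power = Φ(0.653) = 74.3%.

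At 36 per arm, single-visit power is 50% unadjusted and 62% adjusted.

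**The case against.** The strongest reply is that nothing in 10(b) is miscalculated: 44 per arm does give 80% on the stated inputs. That stands. The fault is that the inputs describe a different analysis.

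A reader might go further and infer that the design cannot reach 80% power, or that more patients are needed. The documents do not support either. With the same patients and visits, a baseline-adjusted four-visit mean has about 94% power at 44 per arm, and section 10(a)(iii) already names ANCOVA. But naming it without covariates or a primary contrast does not let the sponsor claim that power yet.

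A reader might also infer that counting baseline among the five measurements dilutes the effect badly. That would require an analysis that averages the baseline value into the outcome, which no section plans. For the endpoint in section 5(d), going from five visits to four costs under 2 percentage points.

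The steeper loss figures (77% to 66%) treat leaving patients as contributing nothing. The plan states no such rule, and patients who exit keep their earlier visits. Using partial data, the erosion is modest. Whether stationary BIA stops on exit is not clearly settled either.

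Finally, 10(a)(i) speaks of noninferiority, whose power cannot be computed without a margin. That is so, but it does not rescue the 80%: no margin is given, and 10(b) is itself stated as power "to detect a difference of 1.676 in a design with 5 repeated measurements".

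**Conclusion.** Wrong as written. The 80% in 10(b) is the power of a two-sided test of a five-measurement average, and the plan does not describe that test. For the comparison it does describe, at each time point, power with no loss at 44–45 per arm is about 59–60% unadjusted and 71–72% baseline-adjusted. The unadjusted figure holds whether the SD is of raw values or of changes; the adjusted one assumes raw values. All figures take the protocol's difference, SD, correlation and compound symmetry as given, and treat the comparison as a two-sided test of a difference.

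The visit count alone is a minor loss. The 2% allowance for loss is thin, but its effect can be given only as a range, since it depends on an exit rate and a missing-data rule that the documents do not supply. Because exit follows from reaching body composition goals, it is also informative. That is a risk of bias which none of these power figures captures.

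**What to change.** Keep 90 patients and make these changes to section 10:

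- Name the primary contrast: the baseline-adjusted difference between arms in the mean of the four post-baseline visits, by ANCOVA or a mixed model, using all available visits. State how primary-outcome data after exit to surgery are handled, given that exit is related to the outcome.
- Restate 10(b) for that contrast. If 3.610 is the SD of raw values, power is about 94% at 44 per arm and 90% at 36, and 28 per arm suffice for 80%. Say which outcome the difference and SD refer to, and whether the SD is of raw values or changes. If it is of changes, recompute the adjusted figures with the appropriate correlation with baseline.
- Add a sensitivity table at 10%, 20% and 30% loss, labelled as assumed.
- State single-visit power (about 59% unadjusted and 71% adjusted at 44 per arm; 50% and 62% at 36) and label the single-visit comparisons supportive.

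The cost is rewriting one paragraph of the power statement and fixing the primary contrast to match. The downside is that the stated single-visit power becomes less favourable.

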 - (a) Patients will be provided a BIA wearable (InBody BAND 2) and instructions regarding downloading smartphone app. Education regarding the device and app will be provided. In addition, they will receive the standard procedures/education provided in arthroplasty-obesity clinic
 - (2) Control group
 - (a) They will receive the standard procedures /education provided in arthroplasty-obesity clinic
- g) Describe all study assessments and activities
 - i) Provide a thorough, detailed description
 - (1) Randomization
 - (a) Once enrolled, patients will be randomized by a non-PI study member. Randomization will occur after the clinic standard education as to not be influenced based on randomization group.
 - (2) All patients
 - (a) All patients will experience a “coaching” period and be eligible for a “surgical period”. All patients (study and control) will undergo the clinic standard operating procedures of stationary BIA, hand-grip strength, and exercise and nutritional education (weight/resistance training, low carbohydrate/high protein diet) in the “coaching” period. All patients will also be advised of the goal to maintain or lose body mass, lose body fat, and gain muscle mass, which is also clinic standard operating procedure. Patients will follow-up in the clinic per standard protocol at approximately every 3 months (± 1 month). At each visit, stationary BIA, hand-grip strength, and exercise and nutritional coaching will be repeated, as is standard in clinic. All patients will be eligible to be indicated for TJA at the PI’s discretion. Per clinic procedures, patients are indicated for TJA as they achieve their body composition goals (maintain or lose body mass, lose body fat, and gain muscle mass). All patients will be instructed to not discuss their study arm (wearable or control) with the PI. Patients are eligible to enter the surgical period at any point during the coaching period. If patients feel that they meet their goals prior to they are eligible to reschedule their appointment sooner than the next visit. All patients will receive a phone call from a study team member every 1 month to assess compliance with study arm and check in on perceived progress.
 - (3) Wearable group

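### The stated 80% power belongs to an averaged repeated-measures test of one unnamed outcome; the plan compares arms visit by visit as noninferiority without a margin, and names no lead outcome, contrast or success rule

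*Combined protocol and SAP*

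**What the plan says.** - Section 5(d)(i) gives as primary outcomes: "Muscle mass, body mass, and fat mass changes from baseline at 3-, 6-, 9-, and 12-months". That is three outcomes at four visits, with none ranked first.
- Section 3(b)(ii) states a superiority hypothesis: "The wearable group will exhibit greater desired body composition changes more rapidly than the control group".
- Section 10(a)(i) plans a "Noninferiority comparison of the primary outcome and secondary outcome between the treatment groups at each time points". It refers to the primary outcome in the singular without identifying it, and gives no margin.
- Section 10(a)(iii) adds: "Non-parametric tests such as ANOVA and ANCOVA will be utilized to determine if there is any difference between the two groups". It names no outcome, visit or contrast.
- Section 10(b) states that 44 per arm "achieve 80% power to detect a difference of 1.676 in a design with 5 repeated measurements having a compound symmetry covariance structure". It uses one standard deviation (3.610), one within-subject correlation (0.500) and one alpha (0.050). It gives no unit and no outcome, and does not say what the five measurements are.

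No section gives a testing order, an any-or-all rule across the three outcomes, a primary visit or a division of alpha.

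**The concern.** Three parts of the plan describe different primary tests. The power statement uses a repeated-measures design with a single outcome. The outcome list has three outcomes, each at four visits. The analysis section compares the arms at each visit and asks about noninferiority.

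Two things are at stake. First, the quoted power may not apply to the test that is eventually reported. Secondly, without a margin noninferiority cannot be declared, and declaring it would not show that the wristband helps, which is the trial's question. With no outcome, contrast or success rule fixed in advance, the result presented as primary could be picked after the data are seen, and no later analysis can restore prespecification.

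**Working it through.** **Inputs from section 10(b):** difference 1.676, SD 3.610, correlation 0.500, alpha 0.050, 44 per arm. Sidedness is not stated.

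**Method.** Each analysis multiplies SD² by a variance factor f. Then SE = 3.610·√(2f/44), z = 1.676/SE, power ≈ Φ(z − 1.960), and n per arm for 80% power = 2(1.960 + 0.842)²·3.610²·f/1.676². Everything below assumes complete data and, for averages, a constant effect.

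**Reproducing the stated figure.** For the average of five equally correlated measurements, f = (1 + 4·0.5)/5 = 0.6. SE = 0.596, z = 2.811, power 80.3%, n = 43.7, which rounds up to 44. A noncentral t gives 79.4%. A one-sided test would need 35 per arm, four measurements 46, and one measurement 73. So the figure fits a single two-sided test of a five-measurement average. The averaging and the two-sidedness are inferred from this arithmetic.

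**Two readings of 3.610.** It could be the SD of levels, with correlation 0.5 between levels, or the SD of change from baseline. Under compound symmetry, changes from a shared baseline correlate 0.5 whatever the level correlation r, so the change reading also fits the stated 0.500. In that case r is unknown; I assume 0.7 to 0.95.

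**Variance factors**
- Average of four unadjusted changes: levels reading (1 + 3·0.5)/4 + 1 − 2·0.5 = 0.625; change reading (1 + 3·0.5)/4 = 0.625.
- Average of four, ANCOVA: levels reading 0.625 − 0.5² = 0.375; change reading (0.25 + r)/2.
- One visit, unadjusted change: 1 on either reading, since 2(1 − 0.5) = 1.
- One visit, ANCOVA: levels reading 1 − 0.5² = 0.75; change reading (1 + r)/2.

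| Two-sided 0.05 difference test, 44 per arm | f | z | Power |
|---|---|---|---|
| Average of 5 measurements | 0.600 | 2.811 | 80.3% |
| Average of 4 changes, unadjusted | 0.625 | 2.754 | 78.7% |
| Average of 4, ANCOVA, levels reading | 0.375 | 3.556 | 94.5% |
| Average of 4, ANCOVA, change reading, r = 0.7 / 0.9 / 0.95 | 0.475 / 0.575 / 0.600 | 3.160 / 2.872 / 2.811 | 88.5% / 81.9% / 80.3% |
| One visit, unadjusted change | 1.000 | 2.178 | 58.6% |
| One visit, ANCOVA, levels reading | 0.750 | 2.514 | 71.0% |
| One visit, ANCOVA, change reading, r = 0.7 / 0.9 / 0.95 | 0.850 / 0.950 / 0.975 | 2.362 / 2.234 / 2.205 | 65.6% / 60.8% / 59.7% |

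These figures concern the one unnamed outcome. Power for the other two cannot be computed, because no difference or SD is given for them.

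**Number of candidate results.** 3 outcomes × 4 visits = 12 comparisons. Suppose any significant result counted as success, a rule the plan does not state. Four unadjusted 0.05 tests of one outcome would then have a familywise error of 15.6% if the visit statistics correlate 0.5, and about 11% if they correlate 0.8 (both assumed; 1,000,000 simulated draws).

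**The case against.** The best defence is that section 10(a)(iii) names ANCOVA and section 10(b) specifies a repeated-measures design, so the natural primary analysis is a baseline-adjusted average over follow-up. Read that way, 80% is met or exceeded, and even the unadjusted average of changes has 78.7%. This stands as far as the number goes. A reader might infer that the 80% is wrong, or that it survives on only one interpretation; the table does not support either. But item (iii) does not say that it means this analysis, item (i) describes a different one, and on any reading the outcome is still not identified.

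It can also be said that the single-visit percentages belong to a difference test which the plan does not state, since item (i) is a noninferiority comparison. That is correct: they are what the stated inputs give once the comparison is put in a form that answers the hypothesis. The power of item (i) as written cannot be computed without a margin.

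A reader might also infer that the plan has a badly inflated false-positive rate. The documents do not support that. No section says that one significant result among many is enough, so the 11–16% is conditional on a rule nobody has written down. What is established is that no rule excludes it.

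**Conclusion.** The concern holds as underspecification of the primary test together with a mismatch between the power statement and the stated comparison. The power arithmetic is correct for an averaged test of one outcome, and roughly right for averaged analyses generally: 78.7% for the mean of four changes and 80–94% for an averaged ANCOVA. It does not carry over to comparisons at each visit, where the same inputs give 58.6% unadjusted, 71.0% with baseline adjustment on the levels reading, or 60–66% on the change reading.

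Separately, a noninferiority comparison without a margin cannot answer a superiority hypothesis. Neither that conflict nor the missing outcome, contrast, success rule and alpha rule depends on any assumption of mine. The percentages rest on the normal approximation, complete data, a constant effect for the averages and, on the change reading, an assumed level correlation of 0.7 to 0.95.

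A reader might go further and conclude that the trial is too small. The documents do not establish this: an averaged, baseline-adjusted contrast reaches 80% at 44 per arm under the conditions above.

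**What to change.** 1. In section 10(a)(i), replace the noninferiority comparison with a two-sided difference test.
2. Name one primary outcome and one primary contrast, adjusted for baseline. Do not count baseline as a response: randomised arms are not expected to differ there, so including it dilutes the difference. The contrast closest to the existing calculation is the average over months 3–12. Test the remaining outcomes and visits in a fixed order or with Holm. An average addresses speed of change only indirectly; the secondary outcome of time to the desired changes can carry that part of the hypothesis.
3. In section 10(b), state which outcome 1.676 and 3.610 describe and whether 3.610 is the SD of levels or of change. Then restate the power for the chosen contrast at the planned size. If a single visit is chosen, state the lower figure, about 60–71% with baseline adjustment.

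The cost is plan wording, loss of lead status for two outcomes, and possibly a less favourable stated power. No added enrolment is required.
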